9. RISKS

a. Potential Risks**i. Investigational devices**

N/A

ii. Investigational drugs

N/A

iii. Commercially available drugs, biologics, reagents or chemicals

Tranexamic acid:

Safety: Higher total IV doses (eg, ≥ 50 mg/kg), such as those given perioperatively, may be associated with an increased risk of seizures; lower doses (eg, 1 or 2 g given in the first 8 hours of trauma) do not appear to increase the risk of seizure or venous thromboembolism (CRASH-3 Trial Collaborators 2019; Fillingham 2018a; Lecker 2016; Myles 2017; Sigaut 2014).

Of note, this study will utilize a single 1g dose toward the end of surgery, therefore no risk of these issues would be expected in our study.

Less common side effects such as low blood pressure, nausea and vomiting are also more often seen at the high dose if medication, but may be possible at the low dose as well.

iv. Procedures

Risks of sinus and nasal surgery are reviewed with every patient during informed consent for the surgical procedure itself in the outpatient setting. These risks remain the same regardless of participation in the study. These risks include infection, bleeding, damage to surrounding structures such as the orbit or intracranial cavity, persistent olfactory dysfunction, septal hematoma/perforation, hypoesthesia of

dentition and/or face, need for revision surgery to achieve optimal result, and risks associated with general anesthesia. Patients must accept these risks before being scheduled for elective surgery.

- v. Radioisotopes/radiation-producing machines

N/A

- vi. Physical well-being

The risks to physical well-being are those associated with underlying disease process and indicated surgery as above. Participation in the study does not alter these risks.

- vii. Psychological well-being

The risks to psychological well-being are those associated with underlying disease process and indicated surgery as above. Participation in the study does not alter these risks.

- viii. Economic well-being

The risks to economic well-being are those associated with underlying disease process and indicated surgery as above. Participation in the study does not alter these risks.

- ix. Social well-being

The risks to social well-being are those associated with underlying disease process and indicated surgery as above. Participation in the study does not alter these risks.

- x. Overall evaluation of risk

Low

b. International Research Risk Procedures

N/A

c. Procedures to Minimize Risk

The intervention medication will be administered in the operating room under the supervision of the anesthesia team. Any unexpected side effects will be identified and addressed at that time. As a matter of routine, patients are watched in the recovery unit after surgery for a period of approximately two hours. The half-life of the IV formulation of tranexamic acid is 2 hours, and so any side-effects should be noted prior to discharge home.

To reduce the risk of data breach, data will be coded after the completion of the patient's participation, which will terminate at the first clinical follow-up visit one week after surgery, at which time they will submit their bleeding journal template. Data will be stored only on a encrypted laptop, and if sharing is required will be done through Stanford-sponsored secure data sharing platforms such as Box.

d. Study Conclusion

As above, active individual patient participation terminates at one week postoperatively. All the data necessary for analysis will have been gathered at this time. This data will still be analyzed along with the remainder of the patients until the time of study completion, which is expected to be 6-9 months later once an adequate number of patients have been recruited.

As above, patients will continue to receive the routine standard of care during this study. Epistaxis is expected after sinonasal surgery and is addressed in a variety of ways (observation, holding pressure, nasal sprays, nasal packing, return to OR). The purpose of this study is to determine whether this inherent risk of bleeding can be reduced. All of these interventions are still available and will be used as clinically indicated.

e. Data Safety Monitoring Plan (DSMC)

i. Data and/or events subject to review

Data that will be collected include study-related adverse events (e.g. thrombosis, nausea requiring overnight admission) and any serious adverse events (e.g. death), suspected serious adverse reactions, and unanticipated problems. Outcomes data will be analyzed every 3 months to assess progress toward study endpoints and to ensure no unanticipated risks of study participation.

ii. Person(s) responsible for Data and Safety Monitoring

[name] (PD)

iii. Frequency of DSMB meetings

Meetings will occur quarterly. If deemed necessary by the IRB, written recommendations will be submitted after each meeting, to include plans to continue the study as designed, continue with modification, temporarily suspend, or terminate.

iv. Specific triggers or stopping rules

The study will end when recruitment targets are reached or if interim data analysis demonstrates a statistically significant difference in endpoints between groups. If Suspected Unexpected Serious Adverse Reactions or Unanticipated Problems (UPs) are encountered, the study will be halted and possibly terminated early if the issue cannot be resolved.

v. DSMB Reporting

The outcome of the review will be disseminated to the co-investigators and the IRB.

vi. Will the Protocol Director be the only monitoring entity? (Y/N)

Yes

vii. Will a board, committee, or safety monitor be responsible for study monitoring? (Y/N)

No

f. Risks to Special Populations

N/A

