study in a clinical context if they meet the screening requirements. Screening may occur either at the preoperative visit that is part of the standard of care, or on the morning of surgery during the surgical consent process if the patient decided to schedule surgery remotely without a preoperative visit. For any patients who have their pre-op visit via telehealth instead of in-person, it will still be brought up in the clinical context of that pre-operative visit. If a patient is interested, the patient will receive more information regarding the study details, and if the patient wishes to participate after a full informed consent process, written consent will be obtained. Patients will need to be able to provide voluntary consent; those who cannot will be excluded. Patients will be excluded if they are under 18 years of age, are pregnant or may become pregnant by time of surgery, are prisoners, are international participants, are unable to provide consent, or are non-English speaking. Patients will also be excluded if they have known pro-thrombotic clotting disorders. Other patients that are not specifically targeted but will not necessarily be excluded include employees and students, as long as they are able to provide voluntary consent. Once a patient has had all questions answered and has voluntarily enrolled in the study, the patient will be provided with a bleeding diary template to record the postoperative experience which include VAS evaluation postoperative bleeding and number of gauze changes per day. They will use this diary template daily postoperatively. Patients will be randomized to receive either the study medication (TXA with saline infusion) or not (saline infusion alone). The surgeon will be blinded to this selection. The anesthesiologist will not be blinded. However, the patient's participation in the study will be announced during the surgical time out, and it will be announced that the attending surgeon is blinded to the patient's participation. The patient will undergo general anesthesia and undergo their sinonasal surgery as routine. The study intervention will occur 15 minutes before completion of the surgery. At this time, a 1,000 mg IV dose of tranexamic acid will be added to the saline infusion by the anesthesiologist for patients randomized to the intervention. Patients randomized to placebo will continue to receive their routine infusion of normal saline, which is administered throughout surgery. The anesthesiologist will be asked only to state 'study medication administered' at the time of administration, whether the infusion consists of saline alone or with the addition of TXA. This will be the only way in which the two study arms differ. To standardize patient management, packing materials (e.g. nasopore, surgical, Floseal) will not be used at the end of a surgery. However, if a patient experiencing clinically concerning bleeding at the termination of surgery that requires use of these materials (or the clinically indicated use of a dose of TXA), they will be unblinded, removed from the protocol, and managed accordingly. Patient safety will always take priority. After reversal of anesthesia and extubation, patients will be transported to recovery as per standard of care. They will be discharged home when meeting routine post-anesthesia criteria (tolerating oral intake, control of nausea, control of pain, etc). After discharge home and through the following week leading up to their postoperative visit, all patients will fill out the diary template outlined above to characterize their daily postoperative bleeding. Patients will then follow up for their first postoperative clinic visit one week after surgery which is the standard of care. They will turn in their postoperative bleeding diary entries at this time. Their active obligation at this point is over, but they will always have the right to have their data removed from analysis if they wish to withdraw. They will not be contacted for research purposes after this point in regards to this specific study, but will continue to follow up clinically as per standard of care. They will have no clinic visits exclusively for

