Patients data will be gathered for one week postoperatively and their direct participation will end at the first clinical visit one week after surgery (their data will still be analyzed after that time). The primary endpoint is the patient VAS assessment of postoperative bleeding over the first week, and the patient report of gauze usage over the first week. Secondary endpoints to be evaluated will include the proportion of patient in recovery on whom the nurses contact the on-call resident for assessment with postoperative bleeding, the need for interventions to address postoperative bleeding (cautery, nasal packing, return to OR), and frequency of patient calls to clinic after discharge home with bleeding concerns. If during interim data analysis a significant difference in postoperative bleeding is noted without an increase in adverse events, discussion could be had with the IRB over developing a new standard of care, however we would anticipate continuing with the standard of care through the end of the study.

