10. BENEFITS

Participants in the study may receive direct benefit if the administration of tranexamic acid does indeed reduce postoperative bleeding, and assuming the participant receives tranexamic acid rather than placebo. Because this is not yet proven, and this study is designed to evaluate this, this is a potential benefit and not a certain benefit. Furthermore, if the patient receives placebo, they will receive no benefit, and will have received the routine standard of care.

If the data gathered from the study is able to show a benefit without additional risks with the administration of a dose of tranexamic acid, then future patients may benefit from this knowledge with a change in the routine standard of care. Given that this type of surgery is one of the most common in the United States, many future patients may have a more favorable postoperative course if the volume of bleeding is able to be reduced effectively.

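### Section 9.c infers from a 2-hour half-life that side effects will be seen before discharge; this does not follow, and no described procedure seeks non-bleeding adverse events afterwards

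*Combined protocol and SAP*

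**What the plan says.** Section 9.c (Procedures to Minimize Risk) states that "patients are watched in the recovery unit after surgery for a period of approximately two hours", and then draws its conclusion: "The half-life of the IV formulation of tranexamic acid is 2 hours, and so any side-effects should be noted prior to discharge home". Section 2.a gives the time of dosing: "The study intervention will occur 15 minutes before completion of the surgery". It sets discharge by criteria, with no fixed time: "They will be discharged home when meeting routine post-anesthesia criteria".

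Section 9.e.i lists what is subject to safety review: "study-related adverse events (e.g. thrombosis, nausea requiring overnight admission"), together with serious adverse events, suspected serious adverse reactions and unanticipated problems. Section 9.a.iii names seizure, venous thromboembolism, low blood pressure, nausea and vomiting in its discussion of drug risk.

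After discharge, section 2.a describes a patient diary, "which include VAS evaluation postoperative bleeding and number of gauze changes per day", a records query for bleeding-related calls, and records of packing, cautery and return to the operating room. A standard-of-care clinic visit follows at one week, and section 9.d places the end of data gathering there.

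The adverse-event data have a stated use. Section 2.g says that a new standard of care could be discussed with the IRB if "a significant difference in postoperative bleeding is noted without an increase in adverse events". Section 10 speaks of a possible change in routine care if the study "is able to show a benefit without additional risks".

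**The concern.** The 9.c sentence treats one half-life of observation as enough to reveal any side effect. If that were right, little would be lost by having no procedure for finding adverse events at home. If it is wrong, the plan needs such a procedure, and sections 2.a and 9 do not describe one.

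What is at stake is the safety half of the benefit-risk statement. Bleeding is sought daily and systematically for a week. Thrombosis, which section 3.a calls a main theoretical concern with this drug, would come to light after discharge only if the patient or a treating clinician happened to raise it. A finding of no increase would then partly reflect how events were found.

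**Working it through.** **Step 1: does the half-life support the inference?** The documents give no derived figure here, so there is nothing to reproduce. The inputs are a half-life of 2 h and a recovery stay of about 2 h (both section 9.c), and a dose 15 minutes before the end of surgery (section 2.a).

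- Dose to end of observation: 0.25 h + 2 h = 2.25 h.
- Fraction remaining under first-order elimination: 0.5^(t/2).
- At 2.25 h: 0.5^(2.25/2) = 0.459, about 46%.
- At 2 h: 0.5^(2/2) = 0.50.
- If the stay is 1.5 to 2.5 h (my assumption for the word approximately), t runs from 1.75 to 2.75 h and the fraction from 0.545 to 0.386.
- Time until less than 10% remains: 2 × ln(10)/ln(2) = 6.6 h. Until less than 5% remains: 2 × ln(20)/ln(2) = 8.6 h.

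This treats the dose as given at one moment. The drug is added to the saline infusion and no infusion time is stated; a slower infusion would leave more at the end of observation.

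**Step 2: is drug level the right measure?** Only in part. Even complete elimination would not fix the time at which an event is recognised. That thrombosis may become apparent later than about two hours is reasoning, not a figure in the documents. For scale, 2.25 h is 2.25/168 = 1.3% of the one-week participation period.

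**Step 3: what is sought after discharge?** Set side by side:

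| Procedure (section 2.a) | What it captures |
|---|---|
| Diary | Bleeding VAS, gauze changes |
| Call query | Calls about bleeding |
| Intervention records | Packing, cautery, return to the operating room |
| One-week visit | Diary handed in; no adverse-event form or question described |

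None of these is described as seeking thrombosis, seizure, admission or nausea. Section 9.e.i says which events are collected, but not how, over what period or by whom they are sought.

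**Step 4: what could be said with full capture?** Section 2.a plans 118 per group; section 8.a plans about 250 in total, or 125 per group at 1:1. With zero events among n treated patients, the exact one-sided 95% upper limit is 1 − 0.05^(1/n):

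- n = 118: 2.51%
- n = 125: 2.37%

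The upper end of a two-sided exact 95% interval, 1 − 0.025^(1/n), is 3.08% and 2.91%. These limits show how far a zero count can be read. They do not measure the capture gap.

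**The case against.** The strongest reply is that section 9.e.i already commits the study to collecting thrombosis and every serious adverse event, with quarterly review and no cut-off at discharge, and that every patient is due in clinic at one week. That stands. A reader might infer that nobody looks for adverse events after discharge; the documents do not support this. What is missing is a stated method and window.

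A reader might also take section 9.c as a rule that closes collection at discharge. It is not. It is a rationale under risk minimisation, worded as an expectation, and nothing in 9.e.i refers to it.

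Nor do sections 2.g and 10 set up a formal safety conclusion. Section 2.g describes a possible discussion with the IRB and expects the standard of care to continue to the end of the study. Section 10 is a conditional remark about future patients. Neither is an endpoint or a test, and section 10 does not need rewriting on this account.

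Finally, the 46% figure does not say how many events would be missed. That is correct. It shows only that the stated reason does not carry the stated conclusion.

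The reply leaves two things unanswered: the 9.c inference is unsound, and the described procedures leave non-bleeding events after discharge to passive reporting.

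**Conclusion.** The point holds in this limited form and should be acted on. On the plan's own figures about 46% of the drug remains when observation ends (39 to 55% over the assumed range of stays), so the half-life cannot support the claim that any side effects should be noted before discharge. Because no method of finding adverse events after discharge is described, the adverse-event condition in section 2.g could rest on what happens to be reported.

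The size of the resulting under-count is unknown, and the documents give nothing from which to estimate it. The conclusion assumes first-order elimination at the stated half-life, and that the documents describe all the post-discharge procedures intended. If a separate adverse-event form exists, it need only be cited and its window stated.

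**What to change.** 1. **Section 9.c:** delete the inference from half-life to detection before discharge, or qualify it so that it makes no claim about later events. This is a change to the reasoning only; it proposes no change to observation or discharge.
2. **Sections 2.a and 9.e.i:** at the existing one-week visit, complete a short fixed adverse-event checklist covering the events named in 9.e.i and 9.a.iii. Use the same form in both arms, completed by someone blind to arm, and state that the window is the day of surgery to that visit.
3. **Section 2.a, records query:** add thrombosis, seizure, and overnight or repeat admission, over the same week and in both arms.
4. **Reporting:** tabulate adverse events by arm with exact 95% confidence intervals, and read the section 2.g condition against that table. State that zero events in 118 to 125 treated patients still leaves a one-sided 95% upper limit of about 2.4 to 2.5%.

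The cost is one short form for each of about 250 patients at a visit that already takes place, the time of a blinded person to complete it, and a few more query terms. No extra visits or patients are needed. The safety statement will be more guarded than a bare report of no increase.

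### Section 9.e.i lists non-serious adverse events only as study-related and names no blinded judge of relatedness, so the adverse-event comparison is open to differential attribution and may miss the low-dose effects the plan names

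*Combined protocol and SAP*

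**What the plan says.** Section 9.e.i defines the safety data: "Data that will be collected include study-related adverse events (e.g. thrombosis, nausea requiring overnight admission) and any serious adverse events", followed by suspected serious adverse reactions and unanticipated problems. Relatedness has no named assessor, no criteria and no statement on blinding. The plan describes no adverse-event form, grading or list of solicited events. The patient diary in section 2.a covers the bleeding VAS and gauze changes.

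Section 9.a.iii names "Less common side effects such as low blood pressure, nausea and vomiting". It says these are seen more often at high doses, "but may be possible at the low dose as well".

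On blinding, section 2.a says "The surgeon will be blinded to this selection" but "The anesthesiologist will not be blinded". On the control arm it says "Patients randomized to placebo will continue to receive their routine infusion of normal saline, which is administered throughout surgery".

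On use of the data, section 2.g says that if at an interim analysis "a significant difference in postoperative bleeding is noted without an increase in adverse events", a new standard of care could be discussed with the IRB. Section 10 ties a change in practice to a benefit shown without added risk.

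**The concern.** A comparison of adverse events between arms is fair if events enter the record by the same rule in both arms. Here the entry rule for non-serious events is a causal judgement. For anyone who knows the arm, that judgement differs by arm almost automatically: control patients received nothing that could have caused a study-related event. Section 9.c relies on the anesthesia team to spot side effects in the operating room, and that team includes the person who knows the arm.

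A second weakness is the gap between the risks named and the events illustrated. Section 9.a.iii names three effects without a severity level. Section 9.e.i mentions only nausea, at overnight-admission level, and omits low blood pressure and vomiting.

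What is at stake is any statement that tranexamic acid reduced bleeding with no rise in adverse events. A filter by attribution could create a false increase or hide a true one. Recording only severe cases could leave too few events to show anything.

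**Working it through.** **1. The plan's own figure.** Section 2.a gives 118 patients per group for 30% v 15%, two-sided 0.05, 80% power. With unpooled variance: (1.960 + 0.842)² × (0.30×0.70 + 0.15×0.85) / 0.15² = 117.7, so 118. This reproduces. It serves below only as the number per arm and does not change.

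**2. The passages side by side.**

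| Event | Condition for collection in 9.e.i | Depends on attribution? |
|---|---|---|
| Any serious adverse event | None | No |
| Unanticipated problem | Own category | Not through the study-related label |
| Non-serious nausea | Study-related; example is overnight admission | Yes |
| Non-serious vomiting or low blood pressure | Not named; enters only if called study-related | Yes |

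The last two rows hold the effects that section 9.a.iii names for this dose.

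**3. What differential attribution could do (all rates assumed).** Let p be the true event rate, equal in both arms, and a₁ and a₀ the proportions called study-related on tranexamic acid and saline. Recorded rates are q₁ = p·a₁ and q₀ = p·a₀. With n = 118 and q̄ the mean of q₁ and q₀, the chance of a significant difference in the direction of the imbalance is

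Φ{ [√n·|q₁ − q₀| − 1.960·√(2q̄(1 − q̄))] / √(q₁(1 − q₁) + q₀(1 − q₀)) }.

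For p = 20% and attribution 50% v 25%, the recorded rates are 10% v 5%. This gives (0.543 − 0.730)/0.371 = −0.504, and Φ = 31%.

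| True rate, both arms | Attribution 50% v 50% | 50% v 25% | 50% v 10% |
|---|---|---|---|
| 10% | 2.5% | 17% | 44% |
| 20% | 2.5% | 31% | 74% |
| 30% | 2.5% | 45% | 90% |

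With attribution reversed (25% v 50%), the same 17% to 45% becomes the chance of a false deficit on tranexamic acid. With equal attribution there is no bias, only lost events.

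**4. What a severity filter could do (all rates assumed).** Here f is the fraction of nausea cases that lead to admission. Expected recorded events per 118 patients, with power from the same formula:

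| Recorded | True 30% v 15% | Power | True 30% v 20% | Power |
|---|---|---|---|---|
| All nausea | 35.4 v 17.7 | 79% | 35.4 v 23.6 | 43% |
| f = 20% | 7.1 v 3.5 | 20% | 7.1 v 4.7 | 10% |
| f = 10% | 3.5 v 1.8 | 12% | 3.5 v 2.4 | 7% |
| f = 5% | 1.8 v 0.9 | 8% | 1.8 v 1.2 | 5% |

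The normal approximation is crude at such small counts, so the event counts are the safer guide.

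Steps 3 and 4 are alternatives. Step 3 assumes events of any severity can be recorded, and step 4 assumes that only admissions are. They cannot both describe one recording rule and should not be combined.

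**The case against.** The strongest reply is that the text does not say the worst of this.

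- The sentence in 9.e.i is worded as inclusive and its cases are examples. An example is not a threshold: ordinary nausea or low blood pressure judged study-related could be recorded. Section 9.c also expects side effects to be noted before discharge. A reader might infer that milder events are excluded, but the documents do not support that. They support only that such events have no defined capture, since 9.c describes clinical observation and not trial data.
- A reader might infer that the unblinded anesthesiologist decides relatedness and that the comparison is therefore biased. No section assigns that task to the anesthesiologist. The surgeon and the residents who evaluate bleeding are blinded. The Protocol Director is the sole monitor, and the plan does not say whether that person knows the arm. A blinded judge would have no basis for attributing differently.
- The anesthesiologist's knowledge bears mainly on low blood pressure. Nausea would arise mainly in recovery, and nothing says recovery staff know the arm.
- Section 2.g is a conditional remark about a possible IRB discussion, without a test or margin, and section 10 is a general statement of benefit. The safety stopping rule in 9.e.iv uses suspected unexpected serious reactions and unanticipated problems, which 9.e.i does not pass through the study-related label.

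All four points stand as limits on the conclusion. They do not remove the gap: the plan conditions collection of non-serious events on a causal judgement and does not make that judgement blind.

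**Conclusion.** The concern holds as a weakness in the collection rule. Non-serious events are listed only through attribution, no blinded assessor is named, and the low-dose effects in 9.a.iii have no defined capture. A conclusion of no increase in adverse events would be weakly supported. The comparison is open to bias in either direction and may miss the named effects. Bias is not demonstrated, and neither is a loss of events.

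Its size cannot be derived from the documents, which give no adverse-event rates and no attribution rates. The figures in steps 3 and 4 show what is possible over a range of assumptions. Step 3 also requires that whoever judges relatedness knows the arm, or is influenced by someone who does. The bleeding endpoints and the sample size are unaffected. This is an inexpensive improvement that should be made before data accrue, because relatedness cannot reliably be rated blind once the arms are known.

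**What to change.** In section 9.e.i:

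1. Remove study-relatedness as a condition for collection. In both arms, record adverse events regardless of attribution from study drug administration to the one-week visit. The announcement that section 2.a requires in both arms gives a common starting time.
2. Take low blood pressure, nausea and vomiting from the routine anesthesia and recovery-unit records in both arms. This assumes those records document them; section 2.a already makes control of nausea a discharge criterion. Write down before abstraction how each effect is counted, identically for both arms.
3. Keep relatedness as a separate field, rated by someone already on the study who is blinded to arm, such as the surgeon.
4. In sections 2.g and 10, base any statement of no increase in adverse events on all recorded events by randomised arm.

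The cost is protocol wording, modest chart abstraction for the roughly 250 patients in section 8.a, and more non-serious events to list. No visit, procedure or clinical management changes. One limitation remains and should be stated: intraoperative low blood pressure would still be charted by the unblinded anesthesia team.
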